6.3 Assignment to study groups

The principal investigator [name] [name] prepares a treatment list and enrolled participants are consecutively entered into this list. The treatment list is prepared beforehand by a (excel) computer-based randomization and cannot be changed.

6.4 Criteria for withdrawal / discontinuation of participants

Participants might have to be excluded, in case of:

- Non-compliance
- Intolerable gastrointestinal effects (diarrhoea)
- Need for systemic antibiotic therapy
- Any other non-foreseeable adverse events

In case of discontinuation, already collected biological and health-related data will be used for analysis, except if the person concerned wishes to be excluded from analysis altogether. Encryption will be maintained at all times.

7. STUDY INTERVENTION

7.1 Identity of Investigational Products

7.1.1 Experimental Intervention (treatment / medical device)

Participants will be randomized to one of the three groups: control-group (1), xylitol group (2) or erythritol group (3). They will then get pre-portioned sticks of either xylitol (24g/d; 3x8g) or erythritol (36g/d; 3x12g) or no food supplement (control-group).

7.1.2 Control Intervention (standard/routine/comparator treatment / medical device)

The control-group receives no food supplement.

7.1.3 Packaging, Labelling and Supply (re-supply)

The two polyols xylitol and erythritol are given to the participants in form of sticks (such as sugar sticks) which are labelled with "Poly-Gut Study" and A or B. Sticks labelled with "A" contain 8g of xylitol and sticks labelled with "B" contain 12g of erythritol. The participant receives a whole batch of the respective portions for the whole study. This batch includes some extra portions, in case a portion is lost and in case the time gap at the end of the study has to be bridged until the final visit.

Effect of the natural sweeteners erythritol and xylitol on vascular function in obese volunteers:

A pilot study, Version 1, 11.4.2016, Version 2, 6.6.2016, Version

7.1.4 Storage Conditions

Polyols are temperature stable, but have to be stored in a dry space. After the study the remaining sticks are returned to the study personnel and are destroyed after counting.

7.2 Administration of experimental and control interventions

7.2.1 Experimental Intervention

1st week= adaption week; run-in: with increasing doses of sweetener:

During the first week, the participants assigned to one of the polyol-groups start with a low dose and then step up so that the gastrointestinal tract can adapt to the new substance. The whole portion is dissolved in some tap water (e.g. 1/2 dl or less) and ingested before the main meals (breakfast, lunch, dinner). In case the participant has forgotten one portion, he/she can take two portions at once without any problems.

- The first 2 days, the participant takes one portion per day (one portion in the morning)
- The next 3 days, the participant takes 2 portions per day (one portion in the morning, one at lunch)
- Then the participant takes 3 portions per day (one portion in the morning, one at lunch and one in the evening) till the end of the study (last visit). This last visit date will already be arranged at the beginning and will be max. 3 days after the 49 treatment days. The participants will get extra sweetener sticks in order to bridge the time gap (49+3 days).

7.2.2 Control Intervention

Participants assigned to the control-group get no sweetener, but will also go through all assessments.

7.3 Dose / Device modifications

In case the participant has forgotten one portion, he/she can take two portions at once without any problems. The participant cannot change the intake schedule and dosage. In case the polyol is not tolerated well (gastrointestinal symptoms), the study has to be discontinued.

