	- Intake of proton pump inhibitors (F Pis) on a regular basis - Intake of antibiotics within the last 3 months before inclusion
	- Intake of pro or prebiotics
	- Chronical diseases of the gastrointestinal tract, history of gastrointestinal surgery with
	major changes to the gastrointestinal tract - Substance abuse, alcohol abuse.
	- Substance abuse, accord abuse Inability to follow procedures due to psychological disorders, dementia or insufficient
	knowledge of project language (German).
	Over a period of 7 weeks, volunteers will ingest the natural sweetener xylitol or erythritol
Measurements and	(or no additional sweetener). Once before and after these 7 weeks we will carry out an
procedures:	oral glucose tolerance test, examine faeces and urine (gut microbiota and metabolomics)
	and take blood samples to analyse lipid profile and liver enzymes. Volunteers will fill in
	a food diary and a questionnaire for gastrointestinal symptoms. The whole study will take
	approximately 8 weeks.
Otrode Due doot /	Randomization to the three study arms will be done by a computer based randomization
Study Product /	(excel). The control group will not receive any sweetener.
Intervention:	The two intervention groups will receive either xylitol or erythritol as follows:
	1st week = run-in (adaption week)
	- 2 days 1 *portion per day (1-0-0)
	- 3 days 2 portions per day (1-1-0)
	- 2 days 3 portions /day (1-1-1)
	2nd to 7th week: Over four weeks the volunteers will ingest 3 portions/day.
	*1 portion xylitol = 8g, 1 portion erythritol = 12g
Control Intervention	We will compare
	a) Baseline findings to post treatment findings. In this way each volunteer will serve as
	his/her own control.
	b) A control group will show whether findings are stable within a participant over 7 weeks.
Number of	In total will enrol 60 volunteers, of which 20 will be controls, 20 will be treated with xylitol
Participants with	and 20 erythritol. This is a pilot trial and a power analysis is not possible. However, we
Rationale:	assume that a relevant difference between the treatments should be observed in 20
-	subjects in each group.
Study Duration:	We plan to carry out this trial within approximately 1 year, starting in August 2016 till
	October 2018, depending on recruitment.
Study Schedule:	Month Year of First-Participant-In (planned): 1st August, 2016
Investigates/a	Month Year of Last-Participant-Out (planned): 1st October, 2018
Investigator(s):	[name] [name]

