	Address: St. Claraspital, Abteilung für Forschung
	[name]
	Email: [contact]
	[contact]

Study Centre(s):	Single-centre
Statistical Considerations:	We will compare a) baseline findings to post treatment findings. In this way each volunteer will serve as his/her own control. In addition, b) a control group will show whether findings are stable within a participant over 7 weeks. This is a pilot trial and a power analysis is not possible. However, we assume that a relevant difference between the treatments should be observed in 20 subjects in each group.
GCP Statement:	This study will be conducted in compliance with the protocol, the current version of the Declaration of Helsinki, the ICH-GCP as well as all national legal and regulatory requirements.
Risk-Benefit statement:	The excessive consumption of erythritol and xylitol can lead to bloating or diarrhoea in sensitive patients. The dosage at which these problems occur varies from person to person, but in most cases single dosage has to exceed 20g per portion or exceed 50g per day. The given dosage in the study will be spread out over the day and we do not anticipate any problems. In previous research, the body was shown to have acclimatised itself to the substances within a few days. The participants are subject to only minimal risk during this study, such as through the blood collection. At the puncture site, swelling, reddening or hematoma can occur, which usually resolves after a couple of days. In rare cases, a local infection or local thrombophlebitis can occur at the puncture site.

STUDY SUMMARY IN LOCAL LANGUAGE

Sponsor	Abteilung für Forschung, St. Claraspital Basel
Principal Investigator	[name] [name] Abteilung für Forschung St. Claraspital Basel [name] [contact] Email: [contact]
Study Title:	Effekt von den natürlichen Süssungsmitteln Erythrit und Xylit auf die Darmbakterien und den Zuckerstoffwechsel bei übergewichtigen Personen: eine Pilotstudie
Short Title / Study ID:	-
Protocol Version and Date:	Version 2, 6.6.2016, Version 3 25.9.2017
Trial registration:	Clinical Trial Gov
Study category:	Risiko Kategorie A gemäss HRO Art.7
Type of Research:	Eine klinische Studie ohne Medikamente oder medizinische Geräte mit niedrigem Risiko unter Verwendung von Nahrungsmittelzusätzen (E967 und E968), bei welchem biologisches Material und gesundheitsbezogene Daten verschlüsselt gesammelt werden.

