Risk-Benefit statement:	Erythrit und Xylit werden in der Lebensmittelindustrie eingesetzt und können bei empfindlichen Personen bei übermässigem Verzehr zu Diarrhoe und Blähungen führen. Die gewählten Dosen sollten, wenn sie wie geplant über den Tag verteilt eingenommen werden und eine Angewöhnungszeit angeboten wird, keine Nebenwirkungen haben. Sollte sich zeigen, dass sich Erythrit und Xylit positiv auf die Glukosetoleranz auswirken, könnten in Zukunft übergewichtige und diabetische Patienten von dieser Süssungsalternative profitieren.

ABBREVIATIONS

AE Adverse Event

CEC Competent Ethics Committee

CRF Case Report Form

ClinO Ordinance on Clinical Trials in Human Research (in German: KlinV, in French: OClin)

CTCAE Common terminology criteria for adverse events

DSUR Development safety update report

GCP Good Clinical Practice
IB Investigator's Brochure
Ho Null hypothesis

H1 Alternative hypothesis

HFG Humanforschungsgesetz (Law on human research)

HMG Heilmittelgesetz

HRA Federal Act on Research involving Human Beings

IMP Investigational Medicinal Product

IIT Investigator-initiated Trial

ISO International Organisation for Standardisation

ITT Intention to treat

KlinV Verordnung über klinische Versuche in der Humanforschung (in English: ClinO, in

French OClin)

LPTh Loi sur les produits thérapeutiques

LRH Loi fédérale relative à la recherche sur l'être humain

MD Medical Device

OClin Ordonnance sur les essais cliniques dans le cadre de la recherche sur l'être humain

(in German : KlinV, in English : ClinO)

PI Principal Investigator
SDV Source Data Verification
SOP Standard Operating Procedure
SPC Summary of product characteristics

SUSAR Suspected Unexpected Serious Adverse Reaction

TMF Trial Master File

SCHEDULE OF ASSESSMENTS (FLOW OF RESEARCH PROJECT)

Project Periods	Screening Visit (V1)	Baseline Metabolic Visit (V2)	Intake of sweetener: • erythritol or xylitol • week 1: adaption					Follow-up Metabolic Visit (V3)		
Location	St. Claraspital	Claraspital	• wee							St. Claraspital
Time (hour, day, week)	-7d	0d	3 x	/day	,					49d
(104., 44), 1104.										+max. 3 days
			Weeks	1				1	1	
			1	2	3	4	5	6	7	
Participant Information and Informed Consent	х									
Demographics: weight, height, abd. circumference	x									х
Medical History	×									
In-/Exclusion Criteria	х									
Randomization		х								
Fasting blood sample	х	х								х
Haemoglobin	х		Ī							
Leucocytes	х		Ī							х
• HbA1C	х									

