2.5 Risks / Benefits

Participants do not profit directly from this study. However, in the long term, findings could lead to a new nutritional concept in obese patients. In sensitive subjects consumption of polyols can lead to borborygmi and diarrhoea. However, if the amount of polyols is distributed over the day - as planned we do not expect intake to cause discomfort. To gain peripheral venous access can be challenging in morbidly obese subjects. Occasionally, blood sampling can result in local skin irritation, hematoma and discomfort. However, well-trained study personnel (used to this special population) will place venous accesses and collect blood samples.

Justification of choice of study population 2.6

In this trial, obese but otherwise healthy volunteers will be included. In morbid obesity virtually all patients suffer from metabolic syndrome with non-alcoholic fatty liver disease, dyslipidaemia and impaired glucose tolerance. In animal models, xylitol consumption led to decrease in visceral fat¹¹ and metabolic syndrome. In a human study carried out on lean subjects in 1982, 3 weeks of xylitol intake showed a decrease in plasma cholesterol values¹⁴.

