4.4 Safety Outcomes

Gastrointestinal tolerance (bloating, diarrhoea etc.): Incidence and severity of gastrointestinal side effects related to the sweetener intake during the study is assessed by using a questionnaire (Clinical rating scale for gastrointestinal symptoms: Svedlund et al.²¹)

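### The forgotten-portion rule permits 24 g of erythritol at once, above the protocol's own 20 g single-dose figure and against the spreading on which its tolerability expectation rests

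*Protocol*

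**What the plan says.** Section 7.3 of the protocol gives the make-up rule: "In case the participant has forgotten one portion, he/she can take two portions at once without any problems". Section 7.2.1 carries the same sentence in its description of the adaption week, just after explaining that participants "start with a low dose and then step up so that the gastrointestinal tract can adapt to the new substance". Neither section limits the rule to one polyol or to the weeks after adaptation.

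Three other places say when gastrointestinal trouble is or is not expected:

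- The Risk-Benefit statement in the synopsis says the dose at which symptoms appear differs between people, but "in most cases single dosage has to exceed 20g per portion or exceed 50g per day". It continues: "The given dosage in the study will be spread out over the day and we do not anticipate any problems".
- Section 2.5 makes the same condition explicit: "However, if the amount of polyols is distributed over the day - as planned we do not expect intake to cause discomfort".
- The Risk-Benefit statement in the German summary adds a period of habituation to the spreading: "Die gewählten Dosen sollten, wenn sie wie geplant über den Tag verteilt eingenommen werden und eine Angewöhnungszeit angeboten wird, keine Nebenwirkungen haben".

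The synopsis fixes the portion sizes ("1 portion erythritol = 12g", and 8 g for xylitol); section 7.1.3 repeats them for the labelled sticks. Section 4.4 makes tolerability a declared safety outcome: "Incidence and severity of gastrointestinal side effects related to the sweetener intake during the study is assessed by using a questionnaire".

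**The concern.** The make-up rule promises freedom from problems for a way of taking the product that the protocol's own risk statement does not cover. The expectation of good tolerance is conditional on spreading the dose, and doubling gives up part of that spreading. In the erythritol arm the doubled intake also passes the only single-dose figure in the protocol. In the xylitol arm it does not, so the rule treats as equal two arms that differ on the protocol's own scale.

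What is at stake is tolerability, not the glycaemic endpoint. Gastrointestinal tolerance is both a secondary and a safety outcome. Under section 7.3 a participant who does not tolerate the polyol must stop, and sections 7.5 and 8.2.5 plan no follow-up visit after that. An instruction that can raise the single dose above the stated figure in one arm only is an avoidable source of symptoms, and of a tolerability difference between the arms that the planned regimen would not produce.

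**Working it through.** **Inputs**

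- Portion size: xylitol 8 g, erythritol 12 g (synopsis; sections 5.1, 7.1.1 and 7.1.3).
- Schedule: days 1–2 one portion, days 3–5 two portions (morning and lunch), from day 6 three portions (section 7.2.1).
- Approximate onset of symptoms: above 20 g in a single dose, or above 50 g per day (synopsis, Risk-Benefit statement).

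**Reproducing the stated daily doses**

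Daily dose = 3 × portion size. Xylitol: 3 × 8 = 24 g. Erythritol: 3 × 12 = 36 g. Both match sections 5.1 and 7.1.1.

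**Doubled intake against the 20 g single-dose figure**

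| Arm | Planned single intake | Doubled intake | Ratio to 20 g |
|---|---|---|---|
| Xylitol | 8 g | 2 × 8 = 16 g | 16/20 = 0.8 (20% below) |
| Erythritol | 12 g | 2 × 12 = 24 g | 24/20 = 1.2 (20% above) |

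**Daily total against the 50 g figure**

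- Made up on the same day, the total is unchanged: 24 g xylitol or 36 g erythritol.
- Carried into the next full-dose day, it is four portions: 4 × 8 = 32 g xylitol or 4 × 12 = 48 g erythritol. Carry-over is an assumption, because the rule does not say whether it is allowed.

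Neither case passes 50 g.

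**Adaption week**

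- Days 3–5, no carry-over needed: a forgotten morning erythritol portion taken with the lunch portion gives 2 × 12 = 24 g at once, the whole day's dose in one intake.
- Day 2, only if carry-over is assumed: a portion forgotten on day 1 and added on day 2 gives 24 g at once where 12 g is planned.

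**Cost of skipping a portion instead**

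Planned portions over 49 days: week 1 = 2 × 1 + 3 × 2 + 2 × 3 = 14; weeks 2–7 = 42 × 3 = 126; total 140. One skipped portion is 1/140 = 0.7%. The up to three bridging days before the last visit are left out.

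**The case against.** The arithmetic is not in dispute. The case on the other side concerns weight.

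- **The 20 g figure is not a limit.** It marks roughly where symptoms begin in most cases, varies between people and is a single figure for both polyols. Exceeding it by 4 g does not show that symptoms will follow. This stands, and it is why the point is minor.
- **The daily figure is never reached.** The dose rationale in section 2.3 gives only a daily figure and mentions trials with up to 200 g per day. This is true, but section 2.3 gives no single-dose size, so it does not support 24 g at once.
- **Doubling abandons spreading only in part.** After a same-day make-up on a full-dose day, the dose is taken in two intakes instead of three, and the rule addresses one forgotten portion. This also stands, although on days 3–5 a double puts the whole day's intake into one.
- **The day-2 example and the 48 g total need carry-over.** They do, and they are marked as assumptions above. The same-day double on days 3–5 does not need it.
- **Other safeguards bound the risk.** Weekly calls, direct telephone access to the investigator, the symptom questionnaire and the stopping rule are all in place. They detect or limit trouble but do not make the sentence correct.
- **A make-up dose can be preferred to a missed one.** Compliance matters greatly to this protocol, so the preference is defensible. It would need a reason why 24 g at once is acceptable, and none is given.

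**Conclusion.** The concern holds and is minor. The make-up rule contradicts the protocol's own risk statement in two ways. In both arms it departs from the spreading on which the expectation of no problems rests. In the erythritol arm it allows a single intake of 24 g against a stated figure of 20 g.

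The mismatch and its arithmetic are certain; harm is not. The protocol gives no rate of forgotten portions and no symptom rate by dose, so the effect on symptoms or drop-out cannot be computed. No effect on the primary outcome is claimed.

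**What to change.** 1. In sections 7.2.1 and 7.3, delete the assurance and replace the rule, for both polyol arms, with: *A forgotten portion is taken later the same day, separately from the next portion, or is skipped. Portions are not doubled and are not carried over to the next day.* A single rule suits both arms because participants are not told which polyol they take (section 5.2.2).
2. In section 7.2.1, state that a late portion need not precede a main meal; otherwise the new rule collides with the instruction to take portions before meals.
3. In section 7.4, add that a single skipped portion is not by itself non-compliance. As written, that section excludes anyone who does not take the sweetener as planned.
4. Make the same change in the participant's study folder if its intake instructions repeat the rule. That appendix is not shown.

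The cost is a few sentences, with no new assessment, form or analysis. The downside is slightly lower total intake when a portion is skipped, 0.7% per portion. A forgotten evening portion will more often be skipped than made up. Under this rule the largest single intake is 12 g of erythritol or 8 g of xylitol, both below 20 g.

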7.4 Compliance with study intervention

Compliance is of uttermost importance in this project. To improve adherence to the intervention, participants are contacted by phone once a week by the study personnel. Apart from answering upcoming questions this allows the study personnel to remind the participant to take the sweeteners regularly, to fill in the questionnaires and to come to the appointments. At the end of the study, the return of unused portions will allow us to estimated compliance. Non-compliance: In case a participant does not take the sweeteners as planned, or fails to fill in the forms and come to the appointments the participant has to be excluded.

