7.5 Data Collection and Follow-up for withdrawn participants

In case a participant wishes to discontinue study participation, the data collected to this time point is included in the analysis. A follow-up visit is not planned in this case.

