8.2.5 Assessments in participants who prematurely stop the study

Participants who discontinue the study are not seen for a follow up visit, as the data obtained after discontinuation will not be useful for our analysis. However, the baseline data will be included in our analyses.

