10.4 Planned Analyses

10.4.1 Datasets to be analysed, analysis populations

In this pilot trial which is purely observational, an analysis per protocol is planned. Drop-outs will be replaced, but baseline data of drop-outs might be included to characterize the baseline population. Baseline values of all three groups will be compared, to rule out any baseline differences. The control group will also be examined twice, and the two time-points should yield similar results. Data from each participant before and after treatment will be analyzed in the sweetener groups. In that way, each participant will serve as his or her own control. Post-treatment values of both treatment groups will then be compared to the control group (without treatment).

In case both sweeteners should have an effect on our endpoints, we might combine the two arms for an additional analysis comparing "no sweetener" (n= 20) vs. "sweetener" (n= 40).

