10.5 Handling of missing data and drop-outs

Missing data: as a basic principle, we will only analyse available data. In case of single missing blood values, a "last observation carried forward" (LOCF) approach will be used. Drop-outs will be replaced. Data from drop-outs will be included in the analysis if feasible (e.g. baseline values can be of value to characterize the study population).

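### Poor polyol tolerance ends participation without a final OGTT and the participant is replaced, so the comparison with control is exposed to a selection that acts only in the sweetener arms

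*Protocol*

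**What the plan says.** All references are to the Protocol.

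- **Removal.** Section 7.3 rules out any change of schedule or dose and continues: "In case the polyol is not tolerated well (gastrointestinal symptoms), the study has to be discontinued". Section 7.4 adds that a participant who "does not take the sweeteners as planned, or fails to fill in the forms and come to the appointments the participant has to be excluded". Section 6.4 lists non-compliance and intolerable gastrointestinal effects more softly, as reasons for which exclusion may be needed.
- **No outcome.** Section 8.2.5: "Participants who discontinue the study are not seen for a follow up visit". Its reason is that "the data obtained after discontinuation will not be useful for our analysis". Section 7.5 also plans no follow-up visit, but it concerns participants who themselves wish to stop.
- **Analysis.** Section 10.4.1: "an analysis per protocol is planned. Drop-outs will be replaced". The same section plans to compare the sweetener arms with the untreated control group on post-treatment values. Section 10.4.2 names one-way ANOVA for group differences, with P < 0.05 as the threshold.
- **Control arm.** Section 7.2.2: controls receive no sweetener and undergo every assessment.
- **Data kept.** Sections 6.4 and 10.5 provide for using data already collected from participants who stop.

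**The concern.** Randomisation takes place at the first metabolic visit (V2, Section 8.3.2), before any sweetener is taken, so everything above happens after allocation. Two of the triggers need a sweetener in order to fire: poor tolerance of the polyol, and not taking it. A control cannot meet either.

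If the participants removed in this way would have had a different OGTT result from those who stay, the difference between arms partly reflects who remained. Replacement restores the number per arm but not comparability, because each replacement must also tolerate and take the product to be counted. A statistical analysis plan written later could not repair this, since an OGTT that was never performed cannot be recovered. The protocol says that its findings will serve to plan larger studies (Section 10.2), so a selected estimate could be carried forward.

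**Working it through.** **Step 1: which exclusions are one-sided.**

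| Reason | Source | Can remove a control? | V3 OGTT lost? |
|---|---|---|---|
| Poor polyol tolerance | 7.3, 6.4 | No | Yes, if before V3 |
| Non-intake noticed before V3 (weekly calls, diary) | 7.4, 5.1 | No | Yes |
| Non-intake found from the stick count at V3 | 7.4, 8.3.5 | No | No; the OGTT is done at that visit |
| Forms or appointments missed | 7.4 | Yes | Depends on timing |
| Systemic antibiotics, other adverse events | 6.4 | Yes | Yes, if before V3 |

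The first two rows are the one-sided loss of outcome. In the third row the result is in hand and only membership of the per-protocol set is in question. The last two rows can apply to any arm and are not at issue.

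**Step 2: do the data-use rules close the gap?** A participant stopped before V3 has a baseline OGTT only. Keeping data already collected (6.4, 10.5) cannot supply the post-treatment OGTT. The carry-forward rule in 10.5 is for single missing blood values.

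**Step 3: possible size.** The protocol gives no expected rate of stopping and no outcome difference, so there is no figure of its own to reproduce. Inputs:

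- n = 20 per arm (Section 10.2); three-group ANOVA at 5% (Section 10.4.2).
- p = share of a sweetener arm removed and replaced: assumed 0 to 20%.
- d = difference between completers and those removed, in SD of the analysed quantity: assumed 0 to 1.0.

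With completer mean m_c and mean m_r in those removed, the mean of all randomised is (1 − p)m_c + p·m_r. The completers-only mean is therefore off by s = p × d:

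- lowest: 0;
- middle: 0.10 × 0.5 = 0.05 SD (or 0.05 × 1.0);
- highest: 0.20 × 1.0 = 0.20 SD.

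Assume no true effect and both sweetener arms shifted alike, so that the group means are 0, s, s. The squared deviations from the grand mean 2s/3 sum to (4/9 + 1/9 + 1/9)s² = (2/3)s². The noncentrality is λ = 20 × (2/3) × s², with F on 2 and 57 degrees of freedom:

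| s (SD) | λ | ANOVA rejects at P < 0.05 |
|---|---|---|
| 0 | 0 | 5.0% |
| 0.05 | 0.033 | 5.2% |
| 0.20 | 0.533 | 9.0% |

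A two-group comparison of 20 with 20 (normal approximation) gives similar figures: 5.3% at 0.05 SD and 9.7% at 0.20 SD.

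**Step 4: replacement.** For 20 completers, 20/(1 − p) must be randomised: 20 at p = 0 and 20/0.80 = 25 at p = 20%.

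**The case against.** The strongest reply is that per protocol is a declared and reasoned choice. The trial is an exploratory pilot, Section 10.1 says that hypothesis testing does not apply, and the expectation is improvement over baseline. The controls mainly show stability over seven weeks, and Section 8.2.5 explains why results off sweetener are not wanted. The protocol also expects good tolerance: both daily doses (24 g and 36 g) are below 50 g, and the first week steps up. Baseline data of drop-outs are kept, so baseline differences between them and completers can be seen.

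Much of this stands. It supports keeping the per-protocol analysis, and it suggests that few will stop. It does not cover the comparison with control, which Section 10.4.1 plans and Section 10.4.2 tests at P < 0.05. Baseline data cannot show whether those removed would have changed differently.

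A reader might go further than the text allows in four ways:

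- **That a single missed portion forces exclusion.** Section 7.4 gives no tolerance, but Sections 7.2.1 and 7.3 allow make-up portions and Section 6.4 is discretionary in tone. A numerical adherence threshold is ordinary analysis-plan detail, so its absence here is no fault.
- **That Section 10.5 admits only baseline values from drop-outs.** It names them as an example.
- **That all imperfect intake costs the OGTT.** The returned sticks are brought to V3, so much of it would surface where the OGTT is done.
- **That the before-after test within an arm measures this problem.** It is also limited to those who remain, but it involves no control and says nothing about a one-sided loss between arms.

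**Conclusion.** The point holds for participants who stop because they do not tolerate the polyol, and for non-intake detected before V3. Sections 7.3, 8.2.5 and 10.4.1 together remove them from the post-treatment comparison by a route closed to controls, and no other section restores the missing result. Who applies the rules does not matter for this.

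The size is unknown and may be small or zero. Under the assumed ranges the ANOVA's false-positive rate is 5.2% at a shift of 0.05 SD, which is negligible. It reaches 9.0% only if 20% are removed, they differ by a full SD, and both sweetener arms shift alike. The removal rate and the outcome difference are assumptions, not protocol figures. This is an improvement worth considering at low cost; the documents do not show that the comparison will be materially biased.

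**What to change.** 1. In Sections 6.4, 7.3 and 7.4, use one wording: stopping the sweetener, or taking it imperfectly, does not end study participation.
2. In Section 8.2.5, invite stopped participants who consent to the V3 OGTT already arranged for them, and word Section 7.5 so that it does not contradict this.
3. In Section 10.4.1, add a between-group comparison of all randomised participants with a V3 OGTT, in their assigned arm. Keep the per-protocol analysis alongside for the on-intake effect. Limit replacement (also in Section 10.5) to those with no V3 OGTT.
4. Report stops and replacements by arm and reason.

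Telling a stopped participant which product was taken (Sections 5.3 and 9.1.3) can stay, because the samples are analysed by blinded personnel (Section 5.2.2).

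The cost is an amendment and a few V3 visits in participants off sweetener. The as-randomised estimate no longer isolates the on-intake effect. If an effect Δ is fully lost after stopping, it becomes (1 − p)Δ, a dilution of up to the share who stopped: 0 to 20% in the assumed range. The retained per-protocol analysis still addresses the on-intake question.
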